### **3.7 Randomization and Blinding**

We will randomize eligible participants through a central electronic system in a 1:1 ratio to lopinavir/ritonavir (intervention) versus placebo (control). A randomized group assignment is provided to the site investigator or delegate from a centralized, web-based platform. Randomization will require provision of the screening number and confirmation of patient eligibility. In the future, we may also consider adding an intervention group.

We will perform the randomization in permuted blocks of varying size and stratified by site and age ( $\geq 65$  years or  $< 65$  years). We will store the randomization sequence allocation on a secure server, which will not be available to site study personnel. Each participant will receive a computer-generated study ID number. The computer-generated study ID number and shipping information will be provided to the pharmacy who will provide a dose pack containing lopinavir/ritonavir or placebo.

The participant, treating clinicians, study personnel, and outcome assessors will all remain blinded to group assignment until after the database is locked and blinded analysis is completed. Only Belmar Pharmacy, who is distributing study medication, and one member of the biostatistical team who is preparing closed DSMB interim reports will be unblinded. Specifically, study medication will be dispensed with packaging and labelling that would blind treatment assignment. Unblinding will occur only if required for subject safety or treatment at the request of the treating clinician.

## **4. STUDY INTERVENTIONS**

### **4.1 Treatment of Study Participants**

A summary of the trial’s schedule of events is included in Appendix A.

Timing of study procedures is based on the time of randomization, which is defined as “Time 0”. Study Day 1 is defined as the day of receipt of the first dose of study drug. We will assess the primary outcome on Study Day 15, which corresponds to 14 days (2 weeks) after the initiation of study drug.

A research physician will prescribe a study medication that a central pharmacy (Belmar Pharmacy) will fill at no charge to the patient and will arrive through overnight mail (typically next day by 10:00AM). The study medication will arrive in blinded blister packs labelled as lopinavir/ritonavir or placebo with the appropriate daily instruction for administration. The goal is initiation of treatment within one day of randomization (Study Day 1).

On Study Days 1-15, the patient will complete brief electronic data collection form through a secure electronic platform that will confirm receipt and administration of study drug and document the number and reason for any missed doses. For those with missing electronic data, telephone follow-up will provide an additional opportunity to clarify study drug administration, as needed. If the participant is hospitalized prior to completion of the study medication, an attempt will be made to continue study medication. However, study medication may be discontinued if felt necessary by the treating clinician in consultation with the local investigator. Unblinding will occur only if required for subject safety or treatment at the request of the treating clinician.

## **4.2 Lopinavir/Ritonavir Group**

Participants assigned to the lopinavir/ritonavir arm will receive lopinavir/ritonavir 400 mg/100 mg orally twice daily for 28 doses (Days 1-14). Medication dose packs will contain all 28 doses labelled by Study Day.

### **Rationale for Drug Selection of Lopinavir/Ritonavir**

We are administering lopinavir/ritonavir (LPR/r) in standard dosing: lopinavir/ritonavir 400 mg/100 mg twice daily for 28 doses (Days 1-14). LPV/r as Kaletra tablets is dosed based upon extensive PK/PD study evaluations in healthy and HIV+ subjects as reported in its US and European labels (400/100mg BID or 800/200mg QD) -

see [https://www.accessdata.fda.gov/drugsatfda\\_docs/label/2016/021251s052\\_021906s046lbl.pdf](https://www.accessdata.fda.gov/drugsatfda_docs/label/2016/021251s052_021906s046lbl.pdf) and <https://www.medicines.org.uk/emc/product/221/smpc>. The mean in vitro antiviral IC50 of lopinavir against HIV in the absence of human serum, is 6.5 nM. The IC50 of LPV vs SARS viruses and in particular SARS-CoV-2 is believed to be approximately 1-10 $\mu$ M. Comparison of these potencies is limited as data are uncontrolled and assay procedure differ, but it suggests SARS-CoV-2 replication is approximately 100 - 1000-fold less susceptible to LPV/r-mediated replication than HIV. PK/PD comparisons across unrelated viral infections with overtly different clinical manifestations also presents significant translational insight limitations, but the safety/efficacy and PK/PD for LPV/r against HIV is well known and enables a guide to a pragmatic and safety-reasoned dosing regimen. A regimen of 400/100 mg BID should achieve near steady state concentrations as seen in HIV therapy within 3 to 4 days. This should align with an acceptable safety profile coupled with rapid achievement of LPV/r exposure to efficacious levels associated with HIV clinical antiviral activity, and possibly some effect on SARS-CoV-2 replication inhibition in patients. LPV/r dosing BID, or 800/200mg QD in adults enables unbound LPV exposure at significantly higher levels than reported by the HIV in vitro antiviral IC50. Multiple dosing with 400/100 mg LPV/r twice daily for 14 days produces mean  $\pm$  SD LPV peak plasma concentration (Cmax) of 12.3  $\pm$  5.4  $\mu$ g/ml. The mean steady-state trough concentration prior to the morning dose was 8.1  $\pm$  5.7  $\mu$ g/ml. LPV AUC over a 12 hour dosing interval averages 113.2  $\pm$  60.5  $\mu$ g/h/m. LPV and RTV are 98–99% bound to the blood plasma proteins, which indicates that unbound LPV exposure to be approximately 10 - 100-fold greater than the in vitro HIV IC50 value, and within an

order of magnitude as reported for SARS-COV-2 value, thereby making clinical testing by the regimen described as reasoned-from a potential antiviral perspective. If unbound drug levels are higher inpatient BAL fluid, then a more favourable ratio is potentially achievable.

### **4.3 Control Group**

Participants randomized to the control group will receive placebo orally twice daily for 14 days. Medication dose packs will contain all 28 doses labelled by Study Day.

While patients who receive the lopinavir/ritonavir will not have a matched placebo, the packaging would indicate study medication (lopinavir/ritonavir, or placebo) and participants will not be aware that there is no matched placebo for lopinavir/ritonavir. Thus, even if the participant searches the internet for pill markings, it is entirely possible from the patient perspective that this could be a matched placebo. Exclusion criteria will be exercised to ensure that two individuals from the same household are not enrolled in the study and that telephone assessments during the study avoid discussion of the appearance of the study medication.

### **4.4 Co-Interventions**

This trial will control the use of lopinavir/ritonavir, or placebo during the 14-day intervention period. Enrolled participants will not receive open-label lopinavir/ritonavir during the 14-day intervention period, unless the patient is hospitalized, and the treating clinician wishes to unblind the trial and use these medications open label. The treating clinicians will make all other treatment decisions without influence from the protocol. Administration of other antiviral, immunomodulatory, or other COVID-19 directed novel medications (“rescue therapy”) will be allowed. We will record the co-administered COVID-19 directed medications in the case report form. The patient will be allowed to take antipyretics at home as needed.

### **4.5 On-Study Monitoring**

All participants enrolled in the study will be outpatients (not hospitalized) and therefore initial monitoring will be remote as part of routine outpatient clinical care with treating physicians and nurses (we anticipate primarily virtual care/telehealth or routine telephone follow-up). The research staff will provide additional remote monitoring through daily electronic collection of symptoms, healthcare utilization, clinically obtained electrocardiograms, newly prescribed medications, and adverse event reporting with supplemental telephone follow-up as needed. The research team may flag potential issues but will defer specific decisions about additional care and hospital transfer to usual outpatient clinical care.

Lopinavir/ritonavir has been used extensively for outpatient treatment of other conditions without the need for additional monitoring during short term therapy.

Between baseline and Study Day 15, study personnel will ascertain and review the initiation of any new medications daily and evaluate for potential medication interactions with lopinavir/ritonavir (see Appendix B). If a medication that is considered to be contraindicated with lopinavir/ritonavir is discovered, site physician investigator or designee will contact the patient to discuss if stopping study drug is appropriate or if the medication in question may be stopped or substituted in consultation with the prescribing/treating clinician. If a medication with a potential interaction with lopinavir/ritonavir is identified, study personnel will contact the treating clinician to ensure they are aware of the potential interaction, as needed. Treating clinicians will determine whether an alternative medication would be

appropriate or whether the risk-benefit ratio favors continuing the medication with the known potential interaction.

#### **4.6 Criteria for Stopping Study Drug**

We will stop administration of the blinded study drug temporarily or permanently for (a) adverse events without evidence of an alternative cause to the patient's symptoms, (b) results of on-study monitoring, or (c) clinical deterioration if requested by treating clinician.

If a patient experiences an adverse event that the patient treating clinicians, or investigators feel merits temporarily or permanently stopping the study drug, we will stop the study drug. We will record the explanation for stopping the study drug in the case report form, and we will record and report the adverse event according to the adverse event guidelines below. If the adverse event resolves to the extent that the patient, treating clinicians, and investigators feel that resuming the study drug is appropriate, we will resume the study drug, and we will record this information in the case report form.

If an EKG is obtained as part of routine clinical care after enrollment and the QTc is greater than or equal to 500 ms, we will discontinue the study drug, unless a repeat EKG after at least 24 hours demonstrates the QTc is less than 500 ms, at which time we will direct the patient to resume the study drug. We will record both the value for the QTc and the decision to continue or stop the study drug in the case report form. If the daily on-study monitoring by study personnel for medication interactions indicates a potential interaction with a medication that treating clinicians feel is required for the optimal treatment of the patient and with which treating clinicians and the investigator feel it would be unsafe to administer lopinavir/ritonavir, we will stop study drug and record the reason in the case report form.

For patients who experience clinical deterioration requiring hospitalization or toxicity potentially related to study drug, for which treating clinicians feel optimal care would include stopping the study drug and unblinding group assignment, we will stop the study drug, and the site investigator will contact the coordinating center to receive the unblinded study group assignment. We will defer any additional treatments to the treating clinicians. In this situation, we will record the following data in the case report form: the criteria met for clinical deterioration; the reason for stopping study drug and unblinding; use of other antivirals, and immunomodulators; and study outcomes. Crossovers from placebo to lopinavir/ritonavir will be recorded and reported to the DSMB at DSMB reviews and interim analyses. The primary analysis will be intention-to-treat.

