### 11.2 Safety Monitoring

Assuring patient safety is an essential component of this protocol. Each participating investigator has primary responsibility for the safety of the individual participants under his or her care. The Investigators will determine daily if any adverse events occur during the period from enrollment through **study day 16** (or 48 hours after completion of the study drug administration) and will determine if such adverse events are reportable. Thereafter, adverse events are not required to be reported to the IRB unless the investigator feels the adverse event was related to study drug or study procedures.

The following adverse events will be considered reportable and thus collected in the adverse event case report forms:

- Serious adverse events
- Non-serious adverse events that are considered by the investigator to be related to study procedures or of uncertain relationship (Appendix C)
- Events leading to permanent discontinuation of study drug.

Study-specific clinical outcomes (Primary, Secondary and Safety Outcomes and Assessments During the Study), including serious outcomes such as organ failures and death, are systematically recorded in the case report forms and are exempt from adverse event reporting unless the investigator deems the event to be related to the administration of study drug or the conduct of study procedures (or of uncertain relationship) as outlined in Appendix C.

After randomization, adverse events must be evaluated by the investigator. If the adverse event is judged to be reportable, as outlined above, then the investigator will report to the VCC their assessment of the

potential relatedness of each adverse event to the study drug or protocol procedure via electronic data entry. Investigators will assess if there is a reasonable possibility that the study procedure caused the event, based on the criteria outlined in Appendix C. Investigators will also consider if the event is unexpected. Unexpected adverse events are events not listed in the study protocol and the investigator brochure for Lopinavir/ritonavir. Investigators will also determine if adverse events are unanticipated given the patient's clinical course, previous medical conditions, and concomitant medications.

If a patient's treatment is discontinued as a result of an adverse event, study site personnel must also report the circumstances and data leading to discontinuation of treatment in the adverse event case report forms.

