## **Appendix C: Adverse Event Reporting and Unanticipated Events**

As noted in section 11, investigators will report all “serious adverse events,” defined as adverse events that are serious and have a reasonable possibility that the event was due to a study drug or procedure (or of uncertain relatedness), to the VCC within 24 hours. The VCC will then notify the single Institutional Review Board (sIRB).

The National/Lead Investigator at the VCC will work collaboratively with the reporting investigator to determine if a serious adverse event has a reasonable possibility of having been caused by the study drug or study procedure, as outlined in 21 CFR 312.32(a)(1), and below. The CC unblinded statistician will also determine if the event is unexpected for lopinavir/ritonavir. An adverse is considered “unexpected” if it is not listed in the investigator brochure or the study protocol (21 CFR 312.32(a)). If a determination is made that a serious adverse event has a reasonable possibility of having been caused by a study procedure or the study drug, it will be classified as a suspected adverse reaction. If the suspected adverse reaction is unexpected, it will be classified as a serious unexpected suspected adverse reaction (SUSAR).

To enhance safety monitoring, the VCC will report every death by coded group (and potentially unblinded group upon request) to the DSMB. The VCC will also report all unexpected deaths, serious and treatment related adverse events, and SUSARs to the DSMB, and sIRB within 7 days after receipt of the report from a clinical site. A written report will be sent to the DSMB and the sIRB within 15 calendar days. The DSMB will also review all reported adverse events and clinical outcomes during scheduled interim analyses. The VCC will distribute the written summary of the DSMB’s periodic review of reported adverse events to the sIRB. The VCC will provide to AbbVie Pharmacovigilance any safety findings for lopinavir/ritonavir (without disclosing protected health information) during the conduct of the trial per contractual language.

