### **C.3. Clinical Outcomes that may be Exempt from Adverse Event Reporting**

Study-specific outcomes of acute respiratory infection, COVID-19, and critical illness will be systematically collected for all patients in both study group and are exempt from adverse event reporting unless the investigator considers the event to be Definitely or Possibly Related (or of an Uncertain Relationship) to the study drug or study procedures. Examples of study-specific clinical outcomes include:

- Death not related to the study procedures.
- Neurological events
  - Seizure
- Cardiovascular events
  - Receipt of vasopressors
  - Atrial or ventricular arrhythmia
  - Cardiac arrest
- Respiratory events
  - Hypoxemia requiring supplemental oxygen
  - Acute respiratory distress syndrome
  - Receipt of mechanical ventilation
  - Receipt of extra-corporeal membrane oxygenation
- Gastrointestinal events
  - Elevation of aspartate aminotransferase or alanine aminotransferase
  - Acute pancreatitis
- Renal events
  - Acute kidney injury
  - Receipt of renal replacement therapy
- Endocrine events
  - Symptomatic hypoglycemia
- Hematologic or coagulation events
  - Neutropenia, lymphopenia, anemia, or thrombocytopenia
- Dermatologic events
  - Severe dermatologic reaction (e.g., Steven's Johnson Syndrome)

Note: A study-specific clinical outcome may also qualify as a reportable adverse event. For example, a ventricular arrhythmia that the investigator considers Definitely or Possibly Related to the study drug would be both recorded as a study-specific clinical outcome and reported as a Serious and Definitely or Possibly Related Adverse Event.

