6.3 Randomization and Blinding

Eligible patients will be randomized in a 1:1 ratio to the intervention arm (lopinavir/ritonavir) or the control arm (placebo). Randomization is stratified by site and age (≥ 65 years versus < 65 years) and uses permuted small block randomization. Patients, treating clinicians, trial personnel, and outcome assessors are blinded to group assignment. Only the investigational pharmacy (who is distributing study medication), the Data Coordinating Center (who is managing the randomization systems including generating the randomization sequence), and one member of the statistical team (who is preparing closed DSMB interim reports) are unblinded.

To maintain the blind, study medication is dispensed with packaging and labelling that does not indicate whether the drug is a placebo or active treatment. Unblinding will occur only if required for subject safety or treatment at the request of the treating clinician and will be done by the

Investigational Pharmacy.

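### Protocol and SAP name different parties to unblind, and an investigator who may know the assignment judges relatedness with no requirement to record it before disclosure

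*Protocol*

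**What the plan says.** **Unblinding.** Protocol 4.6 covers the case that opens "For patients who experience clinical deterioration requiring hospitalization or toxicity potentially related to study drug". If treating clinicians want the drug stopped and the assignment known, "the site investigator will contact the coordinating center to receive the unblinded study group assignment". SAP 6.3 gives the same act to the investigational pharmacy, which is the party named where this excerpt breaks off: "Unblinding will occur only if required for subject safety or treatment at the request of the treating clinician and will be done by the".

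**Who is unblinded.** Protocol 3.7: "Only Belmar Pharmacy, who is distributing study medication, and one member of the biostatistical team who is preparing closed DSMB interim reports will be unblinded". SAP 6.3 lists the pharmacy and one statistician too, but adds "the Data Coordinating Center (who is managing the randomization systems including generating the randomization sequence".

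**Relatedness.** Protocol 11.2 makes primary, secondary and safety outcomes "exempt from adverse event reporting unless the investigator deems the event to be related to the administration of study drug" or study procedures, or of uncertain relationship. Appendix C.3 repeats the rule: "exempt from adverse event reporting unless the investigator considers the event to be Definitely or Possibly Related" or of uncertain relationship. Under 11.2, non-serious events become reportable on the same judgement. The same list also makes SAEs, and events that lead to permanent discontinuation, reportable with no causality condition.

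**Expectedness.** Protocol 11.2 asks investigators to consider whether an event is unexpected. Appendix C adds: "The CC unblinded statistician will also determine if the event is unexpected for lopinavir/ritonavir".

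**The concern.** A site with an urgent request should find one route and one list of people who hold the code. Here the protocol and the SAP give two of each.

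The second matter is who judges causality, and with what knowledge. The role that receives the assignment under 4.6 also makes the relatedness judgement under 11.2 and Appendix C. An investigator told that the participant is on placebo has a reason to answer not related, and one told lopinavir/ritonavir has a reason to answer possibly related. If the judgement follows disclosure, the adverse event label on a study outcome, the decision to report it urgently, and the collection of a non-serious event can all depend on the arm. Expectedness, which completes the classification of a suspected serious reaction as a SUSAR, is partly given to someone who knows the arm by design.

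**Working it through.** No arithmetic applies, so the check is to set the passages side by side.

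**1. Route and code holders**

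| Question | Protocol | SAP |
|---|---|---|
| Who releases the assignment? | Coordinating center (4.6) | Investigational pharmacy (6.3) |
| Who is unblinded? | Pharmacy and one statistician (3.7) | Pharmacy, one statistician and the Data Coordinating Center (6.3) |

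Neither list makes the two routes agree. If Protocol 3.7 is complete, the center as such holds no code. If SAP 6.3 is complete, the Data Coordinating Center could answer a request, but the SAP still gives the task to the pharmacy. The protocol's abbreviations include both a DCC and a VCC, and 4.6 does not say which it means.

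**2. Where relatedness determines reporting**

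| Event | Does the investigator's judgement decide? |
|---|---|
| Study-specific outcome (e.g. arrhythmia, pancreatitis, liver enzyme elevation) | Yes for adverse event reporting (11.2, C.3). No for recording (11.2, C.3) or for the safety analysis (SAP 5.3) |
| Non-serious event outside the outcome list | Yes, unless it leads to permanent discontinuation (11.2) |
| Event leading to permanent discontinuation | No (11.2) |
| SAE | No under the list in 11.2 and the end of 11.3. Yes under the opening of Appendix C |

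Two gaps follow.

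- Section 11.2 does not say which prevails when an exempt outcome is also an SAE or leads to permanent discontinuation: the exemption or the reportable list. The decision tree in Appendix C.4 is a figure that was not available here. If it settles the point, the text should say the same.
- The opening of Appendix C treats reported SAEs as those with a reasonable possibility of being due to drug or procedure, or of uncertain relatedness. Protocol 11.2 and 11.3 report and collect SAEs whatever the view on causation. The 24-hour alert sentence in 11.3 contains both ideas: it covers serious events related to study procedures, yet whatever the suspected cause. SAP 11.1 takes its definitions from Appendix C, so the conflict carries into the SAE table of SAP 11, which otherwise has no relatedness filter.

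**3. Order of judgement and disclosure**

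Protocol 4.6 lists what is recorded at unblinding: the deterioration criteria met, the reason for stopping and unblinding, other antivirals and immunomodulators, and outcomes. Neither relatedness nor the time of disclosure is on the list. No passage in either document requires the judgement to come first or to be made by someone still blinded. A later reader could not tell which judgements were made blind.

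**4. Expectedness**

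Protocol 11.2 and Appendix C use essentially the same test: whether the event is listed in the brochure or protocol. They name different roles and do not say whose answer prevails.

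**5. Size**

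An estimate would need the number of participants unblinded under 4.6, the share of their events judged after disclosure, and the shift in judgement that knowledge of the arm causes. The documents give none of the three.

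**The case against.** A reader might infer that relatedness alone decides whether these events are reported, and so that adverse event capture differs by arm. The documents do not support that.

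- SAEs and events leading to permanent discontinuation have routes in 11.2 with no causality condition, and every unblinding under 4.6 also stops study drug. This stands, with limits: 4.6 allows temporary stops, and precedence over the exemption is not stated.
- Exempt outcomes are recorded for all participants in both arms, and SAP 5.3 names the safety outcomes for analysis without a relatedness condition. Every death goes to the DSMB by coded group, and the DSMB reviews clinical outcomes at scheduled interim analyses. This stands in full. The exposure is to classification, not to loss of the named events.
- The documents give no order of events, and the toxicity trigger in 4.6 already implies a preliminary causal view. This stands too: an unblinded judgement is permitted, not prescribed.

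A reader might also infer that the statistician makes the SUSAR classification. That goes too far. Under Appendix C the lead investigator and the reporting investigator determine causality, and expectedness is largely a check against listed events. Two-level review is a possible reading, although Appendix C does not say it.

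On the route, sites follow the protocol, and the center might relay requests to the pharmacy. Neither document says so. That a site could reach only the DSMB statistician is an inference from 3.7, not something stated.

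**Conclusion.** Four points hold on the text.

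1. Protocol 4.6 and SAP 6.3 name different parties to unblind, and Protocol 3.7 and SAP 6.3 list different unblinded parties.
2. For exempt study outcomes and for non-serious events, an investigator who may know the assignment makes the judgement that determines adverse event classification and reporting, and no prior record is required.
3. Protocol 11.2, 11.3 and Appendix C disagree on whether SAE reporting depends on relatedness, and SAP 11.1 inherits the disagreement.
4. Expectedness is given to two roles, one of them unblinded.

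What is exposed is adverse event labelling, expedited reporting, and non-serious events outside the outcome list, which feed the table of other adverse events in SAP 11. The comparison of the named safety outcomes between arms is not exposed.

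It is tempting to take the hospital categories in the SAP 7 table and apply an unblinding rate to obtain a count. That table shows illustrative status proportions, not cumulative hospitalization, and any rate would be invented. No figure should be attached to this point. It is a worthwhile, low-cost correction. It rests on the two documents alone; a pharmacy manual or DSMB charter may already give an agreed route.

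**What to change.** - **Protocol 3.7, Protocol 4.6, SAP 6.3:** reconcile to one list of unblinded parties and one route. If the center relays requests to the pharmacy, say so and say which center is meant.
- **Protocol 4.6 and 11.2:** require the investigator to record relatedness of the triggering event, with date and time, before the assignment is disclosed. Where disclosure is too urgent, flag the event as judged unblinded. Use the blinded judgement wherever relatedness determines reporting or tabulation.
- **Protocol 11.2, 11.3, Appendix C and SAP 11.1:** state once whether SAE reporting depends on relatedness, and whether the exemption or the SAE and discontinuation items prevail when both apply.
- **Appendix C:** have a blinded medical role decide expectedness against the brochure and protocol, with the statistician only linking the assignment afterwards. Align 11.2 with this.

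None of this changes who may be unblinded, when, or when study drug is stopped. The cost is protocol and SAP wording and a date and time field on the adverse event form. The downside is one short entry before disclosure, and the urgent-case flag keeps it from delaying care.
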